## Actavis LLC

or study procedure is made.

Adverse events will be coded according to MedDRA (Medical Dictionary for Regulatory Activities) and reported with respect to severity, duration, relationship to study medication(s), seriousness and action taken.

## 13.6 Reporting of Serious Adverse Events

To satisfy regulatory requirements, all serious adverse events (as described in Section 1.1) that occur during the study period (including the protocol defined follow up period, described in Section 5.7), regardless of judged relationship to treatment with the study drug, must be reported to the sponsor or CRO by the investigator. The event must be reported within 24 hours of when the investigator learns about it. Completing the serious adverse event form and reporting the event must not be delayed, even if not all the information is available.

## PLEASE NOTE THAT EMAIL IS THE PREFERRED MEANS OF COMMUNICATION.

The CRO should inform PhV if the whole study is early discontinued due to safety reasons.

It is the responsibility of the CRO to report a Serious Adverse Event (SAE) to the FDA within proper time constraints as per the Guidance for Industry and Investigators Safety Reporting Requirements for INDs

and BA/BE Studies- December 2012. Confirmation of submission of this report must then be provided to Actavis, Inc. (Teva)'s study representative as well as their Pharmacovigilance department (contact info below).

The timeliness for submission of expedite reports should be 15 days or 7 days (death cases) or as otherwise specified in local regulations.

All SAE of the study due to safety reasons must be reported in parallel to the following persons:

Sponsor's Contact person for this Biostudy (copy of the SAE details for information purposes only)

Name:

Phone:

Fax: E-mail:

These SAE reports must contain the following information, preferably using the template provided by the Sponsor:

- A. Study name/number
- B. Study Drug
- C. Investigator details (name, phone, fax, e-mail)
- D. Subject Number
- E. Subject Initials when appropriate

Actavis LLC

F. Subject Demographics

G. Clinical Event

- 1) Description
- 2) Date of onset

3) Treatment (drug, dose, dosage form)

4) AE Relationship to study drug

5) Action taken regarding study drug in direct relationship to the AE

H. If the AE was Fatal:

1) Cause of death (whether or not the death was related to study drug)

2) Autopsy findings (if available)

The SAE form and supportive documents should be filled/written in English. The SAE form completion and reporting must not be delayed even if all of the information is not available at the time of the initial contact. Additional information (follow-up) about any SAE unavailable at the initial reporting should be forwarded within 24 hours of the information becoming available to the same address as the initial report. Subjects who have had an SAE during the treatment period must be followed clinically until all parameters (including laboratory) have either returned to normal or have stabilized or are otherwise explained.

Each report of a serious adverse event will be reviewed and evaluated by the investigator and the sponsor pharmacovigilance to assess the nature of the event and the relationship of the event to the study drug, study procedures, and to underlying disease.

Pharmacovigilance local safety officer at Actavis Inc. (Teva) USA will take on the responsibility of reporting SAEs to local authorities (except from US). The CRO will take on the responsibility of reporting SAEs to the investigators and/or to the IRB/Ethics Committee.

The investigator does not need to actively monitor subjects for adverse events once the study has ended. Serious adverse events occurring to a subject after the treatment of that subject has ended should be reported to the sponsor if the investigator becomes aware of them.

[figure not shown]
## Submission of SAEs

Any serious adverse event will be reported to competent authority and ethics committee according to the country specific requirements and the responsibilities defined in the abovementioned section. All AEs will be reported in the Clinical Study Report with the complete information named above according to the requirements of the Note for Guidance on Structure and Content of Clinical Study Reports (CPMP/ICH/137/95).

## Investigator Reporting of SAEs

Adverse events which are evaluated by the Investigator as "Serious" will be reported to the CRO designated below and IRB within 24 hours of notice whether or not they are considered expected or drug-related. All Serious Adverse Events will be reported as per FDA regulations.

Any serious adverse events should be reported to within 24 hours to:

should also copy:

The Investigator or the Investigator's designee must be prepared to supply minimum details needed in the SAE reporting with the following information:

- a. Investigator Name and Site Number
- b. Patient I.D. Number
- c. Patient initials and date of birth
- d. Patient Demographics
- e. Clinical Event
  - 1) Description
  - 2) Date of onset
  - 3) Severity
  - 4) Treatment (including hospitalization)
  - 5) Relationship to study drug
  - 6) Action taken regarding study drug
- f. If the AE was Fatal or Life-threatening
  - 1) Cause of death (whether or not the death was related to study drug)
  - 2) Autopsy findings (if available)
  - 3) Death Certificate
- g. Concomitant medication log
- h. AE log
- i. Relevant tests with dates
- j. IP Unblinding information, if applicable

## CRO Reporting of SAEs

will report any Serious Adverse Event to Actavis Inc. drug safety team and the medical monitor within 1 business day.

## Drug Safety Department:

## Sponsor Study Manager:

## Medical Monitor:

## Actavis LLC

## **13.7 Submission of SAEs**

The Principal Investigator or the Principal Investigator's Designee must complete the provided Serious Adverse Event (SAE) Form (Attachment 1). Actavis LLC. will be responsible for reporting the SAE to the FDA per regulations. Actavis LLC. will provide with a completed MedWatch FDA Form 3500A wherever applicable.

## **13.8 Early Termination**

A subject may terminate from the study early for any reason at any time without any disadvantages. In this case, the investigator should make every effort to have the subject return to the next scheduled visit to perform all required End of Study / Study Completion / Early Termination visit activities and to collect and reconcile all test articles. If the subject does not return for the End of Study / Study Completion / Early Termination visit, the site should fully document the reason for early termination. All data, including the date and primary reason for termination, must be recorded on the End of Study / Study Completion / Early Termination case report form (CRF), and source document.

Any subject who experiences an adverse event may be terminated from the study or from study treatment at any time at the discretion of the investigator. In this case, the subject should be followed at the discretion of the investigator until the resolution or stabilization of the AE. All applicable data should be recorded in the adverse events section of the case report form (CRF). If a subject terminates from the study early for multiple reasons that include adverse events, the End of Study / Study Completion / Early Termination case report form should indicate that early termination was related to an adverse event. An exception to this requirement will be the occurrence of an adverse event that in the opinion of the investigator is not severe enough to warrant early termination but that requires the use of a prohibited medication, thereby requiring discontinuation of the subject. In such a case, the reason for discontinuation would be the need to take a prohibited medication, not the adverse event.

The investigator must inform the clinical project physician/clinical leader/Principal Investigator as soon as possible of all subjects who are being considered for early termination due to adverse events. Additional reports must be provided when requested. The Sponsor reserves the right to terminate the study at any time for administrative reasons. The study may also be terminated by regulatory authorities or by the investigator for his/her site following consultation with the Sponsor. Following a decision to discontinue the trial, the investigator will immediately inform both the study subjects and the IEC responsible for this trial within 10 working days, stating the reasons for discontinuation of the study and, CONFIDENTIAL Page **43** of **63**  furthermore, advise them in writing of any potential risks to the health of study subjects or other persons. It is Sponsor's responsibility to report the premature termination of the study to the regulatory agencies within 15 days providing them with the reasons for the trial discontinuation and advising them in writing of any potential risks to the health of study subjects or other persons. The CRO may notify the regulatory agency on behalf of the Sponsor.

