#### TEST OF EQUIVALENCE:

• The PP population includes all randomized subjects who meet all inclusion and exclusion criteria,

• The safety population includes all randomized subjects who receive study drug.

Subjects who discontinue because of lack of treatment effect after completing two days of treatment should be analyzed in the mITT and PP populations as a treatment failure. Subjects discontinued for other reasons, including drug-related adverse events, should be excluded from the PP population, but included in the mITT population using Last Observation Carried Forward (LOCF).

The recommended primary endpoint is the proportion of subjects with cure at Visit 5 (end of the study on day  $14 \pm 2$  days) defined as a score of 0 for aqueous cells, a score of 0 for aqueous flare and a score of no more than 3 for pain.

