#### 8.6 Unscheduled Visits and Early Discontinuation Visit:

An Unscheduled Visit is allowed at any time, for any reason, if in the Investigator's opinion it is warranted. If the Unscheduled Visit is due to an AE, the Investigator will determine whether additional visits are needed.

If a study subject is discontinued from the study during an Unscheduled Visit, the Unscheduled Visit will be referred to as an Early Discontinuation Visit and all procedures scheduled for Visit 5 will be performed. If the Unscheduled Visit is not an Early Discontinuation Visit (i.e., the study subject will continue to take part in the study), then the reason for unscheduled visit is documented and required procedures at the discretion of CONFIDENTIAL Page 27 of 63 investigator considering the reason for visit, will be performed.

If the study subject's condition has worsened to the degree that it is unsafe for the study subject to continue in the study, the study subject may be discontinued from the study as treatment failure and a standard of care treatment may be advised at the Investigator's discretion.

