Worsening of the disease under study will be measured by evaluation of pain and inflammation. The evaluation of pain and inflammation should be recorded as an adverse event only if the presentation and/or outcome is more severe than would normally be expected from the normal course of the disease in a particular patient.

A treatment-emergent AE is any AE that occurs after initiation of study medication, or any event already present that worsens in either intensity or frequency following exposure to study medication.

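### A severe lack-of-effect failure that is also an adverse event can be coded as an AE withdrawal and leave the per-protocol equivalence set, and no readable rule says which reason takes precedence

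*Protocol*

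**What the plan says.** Four sets of rules bear on the same subject.

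- **When pain or inflammation is an AE.** Protocol 13.1 (Adverse Event) says their evaluation "should be recorded as an adverse event only if the presentation and/or outcome is more severe than would normally be expected".
- **How the reason for leaving is recorded.** Protocol 13.8 asks for the primary reason. It adds: "If a subject terminates from the study early for multiple reasons that include adverse events", the "case report form should indicate that early termination was related to an adverse event". There is one exception. If the AE is not severe enough to warrant termination but needs a prohibited medication, "the reason for discontinuation would be the need to take a prohibited medication, not the adverse event".
- **What the reason does to the analysis.** The protocol synopsis (Test of Equivalence) says: "Subjects who discontinue because of lack of treatment effect after completing two days of treatment should be analyzed in the mITT and PP populations", as failures. It continues: "Subjects discontinued for other reasons, including drug-related adverse events, should be excluded from the PP population", with last observation carried forward (LOCF) in mITT.
- **What worsening does to the analysis.** Protocol 8.6 says that when worsening makes continuation unsafe, "the study subject may be discontinued from the study as treatment failure". Protocol 3.0 and SAP 3.1 also have such a subject evaluated as a failure. Protocol 9.0 instead excludes from PP a subject who worsens and needs alternate or supplemental therapy.

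SAP 7.7.1.1 tests equivalence on PP only. SAP 8 reports no changes from the protocol's analyses. Most of the PP definition in SAP 6.3, and a block after the cure/failure definition in SAP 7.7.1, are redacted.

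**The concern.** An eye with unusually severe post-operative inflammation is the clearest kind of treatment failure. It is also the kind that 13.1 turns into an AE. If the analysis reads the reason from the end-of-study form, an instruction in the safety section decides whether that eye counts as a PP failure or is absent from PP.

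Only failures are lost this way, and only from the analysis that carries the equivalence claim. If the less effective product loses enough more of them, the PP difference shrinks toward zero, and equivalence becomes easier to conclude in the situation the test is meant to detect.

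**Working it through.** **Step 1: follow one subject.** Take a subject who stops after two days of treatment because study-eye inflammation is more severe than expected.

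| Rule applied | PP status |
|---|---|
| Synopsis, lack of treatment effect | In PP, failure |
| Protocol 3.0, 8.6; SAP 3.1, unsafe to continue | Treatment failure |
| Protocol 13.8, reasons include an AE; then synopsis, other reasons | Out of PP |
| Protocol 13.8 exception, prohibited medication; then synopsis, other reasons | Out of PP |
| Protocol 9.0, worsening that needs other therapy | Out of PP |

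Several rows can apply to the same subject, and no readable sentence ranks them. The exception in 13.8 does not restore PP status, because a prohibited medication is also a reason other than lack of effect.

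**Step 2: inputs for size.** The plan gives no withdrawal rates and its sample-size basis is redacted, so it has no figure to reproduce. From the documents: about 450 randomised; a continuity-corrected 90% interval that must lie within [-0.20, +0.20]; and Day 14 inflammation resolution of 65% and 61% on the reference drug in the label appended to the protocol. Assumed: 150 per active arm (450/3; the allocation is redacted), reference cure 0.63 (midway between 0.61 and 0.65, a proxy for cure), test cure 0.43 (exactly at the margin), and the shares removed.

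**Step 3: effect on the difference.** If a share f of an arm is removed and all of those subjects are failures, PP cure is p/(1-f). The PP difference is

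D = 0.43/(1-fT) - 0.63/(1-fR).

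- 5% v 2% removed: 0.4526 - 0.6429 = -0.190
- 10% v 5%: 0.4778 - 0.6632 = -0.185
- 15% v 5%: 0.5059 - 0.6632 = -0.157
- 5% v 5%: 0.4526 - 0.6632 = -0.211

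So D moves toward zero only when fT/(1-fT) exceeds 0.63/0.43 = 1.47 times fR/(1-fR). Some excess in the test arm is needed, not just any removal.

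**Step 4: chance of concluding equivalence at the margin.** The interval is d ± {1.645 × sqrt[pT(1-pT)/nT + pR(1-pR)/nR] + 0.5(1/nT + 1/nR)}. Binomial probabilities are summed over all outcomes whose interval lies within the margin, with PP arm sizes 150(1-f) taken to whole subjects.

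| Removed, test v reference | False equivalence |
|---|---|
| none | 3.5% |
| 5% v 5% | 2.3% |
| 3% v 2% | 3.6% |
| 4% v 2% | 4.4% |
| 15% v 10% | 4.6% |
| 5% v 2% | 5.2% |
| 10% v 5% | 6.3% |
| 15% v 5% | 14.5% |

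A second set of assumptions (0.45 v 0.65) behaves alike. With 150 per arm the figures are 3.5% with none removed, 5.5% at 5% v 2%, 6.6% at 10% v 5% and 2.3% at 5% v 5%. With 180 per arm they are 3.8%, 5.9%, 7.1% and 2.5%.

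**Step 5: one data set.** Suppose 78/150 v 96/150 cured, with every failure kept. Then d = 0.520 - 0.640 = -0.120, 1.645 × 0.0566 = 0.0930, correction 0.0067, and the interval is -0.220 to -0.020: not equivalent. Remove 10 test and 3 reference failures, giving 78/140 v 96/147. Then d = 0.557 - 0.653 = -0.096, 1.645 × 0.0575 = 0.0945, correction 0.0070, and the interval is -0.197 to +0.006: equivalent. The coding of 13 subjects decides the result.

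**The case against.** The best defence is that the PP rule is worded by why the subject left, not by a form code. A subject who leaves because treatment did not work is kept; 'other reasons' means other than that; and under-treated inflammation is hardly a drug-related AE. SAP 3.1 also calls unsafe worsening a failure without mentioning the form. This is a fair reading, but it does not settle the matter. The synopsis excludes other reasons *including* drug-related AEs, so the excluded class is wider than those AEs. Protocol 9.0 excludes some worsening subjects from PP outright.

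Further points stand and limit the concern:

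- A reader might infer that 13.8 codes every multi-reason termination as an AE. It does not. It applies only when one of the reasons is an AE, and it has the prohibited-medication exception.
- A reader might infer that the form erases lack of effect. The text does not say so. Protocol 9.0 has the reasons documented, and the form is not among the documents. Single coding is an inference from the request in 13.8 for a primary reason.
- The redacted text in SAP 6.3 and 7.7.1 may already contain a precedence rule.
- A reader might infer that the rule always favours equivalence. Equal removal works against it, and several modest imbalances leave the error below 5%. The 14.5% needs a threefold imbalance that no passage supports.
- In the Step 5 example the observed -0.120 lies inside the margin, so concluding equivalence there need not be wrong. It shows only that the decision can turn on coding.
- These subjects stay in mITT by LOCF, so the superiority test does not lose them. That does not help equivalence, for which no mITT analysis is planned in the readable text.

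**Conclusion.** The point holds as an unresolved conflict, not as a proven bias. On the readable text, a severe failure that is also an AE can be kept in PP as a failure or dropped from it, and Protocol 9.0 conflicts with the synopsis, 3.0, 8.6 and SAP 3.1 over much the same subjects. At a true difference of -0.20, false equivalence moves from about 3.5% to 5.2% to 14.5% under the larger imbalances shown, and falls to 2.3% with equal removal of 5%. These figures rest on an assumed 150 per arm, assumed cure rates and assumed removal shares. It should be fixed, on condition that the redacted text does not already do so.

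**What to change.** First check the redacted blocks in SAP 6.3 and 7.7.1. If they do not settle precedence:

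1. On the end-of-study form and in Protocol 13.8, record every contributing reason, with lack of treatment effect as its own item.
2. Reconcile the analysis wording of the synopsis (Test of Equivalence), Protocol 3.0, 8.6, 9.0 and 13.8, and SAP 3.1, so that each subject has one analysis status. Decisions on stopping and treating a subject are not touched.
3. State in the protocol and SAP that, for analysis, a subject is a treatment failure in PP and mITT in either of two cases: lack of treatment effect is any recorded reason (after the two days of treatment the synopsis requires), or an AE of study-eye pain or inflammation led to withdrawal. Assign this while masked. The event still counts in the AE tables.
4. Add a sensitivity analysis of equivalence that counts all such withdrawals as failures, including those recorded under prohibited medication or need for other therapy because of study-eye pain or inflammation.

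The cost is a form item, its completion guidance, a few sentences and one extra table, with no added patients or visits. The equivalence estimate may become slightly less favourable. The change should be made before unmasking, because reclassifying subjects afterwards would not be credible.

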## 13.9 Pregnancy

All pregnancies of women participating in the study that occur during the study, or within 30 days of completion of the study, are to be reported immediately to the individual identified in the clinical study personnel contact information section of this protocol, and the investigator must provide the Sponsor with the pregnancy form. The process for reporting a pregnancy is the same as that for reporting a serious adverse event (see 13.8). Any female subject becoming pregnant during the study will discontinue treatment. All subjects who become pregnant will be monitored for the outcome of the pregnancy (including spontaneous or voluntary termination). If the pregnancy continues to term, the outcome (health of the infant up to 8 weeks of age), including details of birth and presence or absence of any birth defect, congenital abnormalities, or maternal and newborn complications, will be reported to the sponsor. Any complication of pregnancy during the study and any complication of pregnancy that the investigator becomes aware of after termination from the study will be reported as an adverse event or serious adverse event, as appropriate.

If the pregnancy does not continue to term, one of the following actions will be taken:

- For a spontaneous abortion, report as a serious adverse event.
- For an elective abortion due to developmental anomalies, report as a serious adverse event.
- For an elective abortion not due to developmental anomalies, report on the pregnancy form; do not report as an adverse event.

## **13.10 Medication Error and Special Situations**

Any administration of medication that is not in accordance with the study protocol should be reported on the CRF, regardless of whether an adverse event occurs as a result.

Types of medication errors and special situations:

- 1. Breastfeeding Suspected adverse reactions which occur in infants following exposure to a medicinal product from breast milk.
- 2. Unexpected Benefits of Drug
- 3. Medication error: Any unintentional error in the prescribing, dispensing, or administration of a medicinal product while in the control of the healthcare professional, patient, or consumer.
- 4. Overdose: Administration of a quantity of a medicinal product given per administration or cumulatively which is above the maximum recommended dose according to the authorized product information. Clinical judgment should always be applied.

- 5. Misuse: Situations where the medicinal product is intentionally and inappropriately used not in accordance with the authorized product information.
- 6. Abuse: Persistent or sporadic, intentional excessive use of medicinal products which is accompanied by harmful physical or psychological effects.
- 7. Off-label use: Situations where a medicinal product is intentionally used for a medical purpose not in accordance with the authorized product information.
- 8. Occupational exposure: Exposure to a medicinal product, as a result of one's professional or non-professional occupation.
- 9. Lack of efficacy

